## **STUDY SYNOPSIS**

### **Interstitial Radioactive Iodine Implants for the Treatment of Pituitary Macroadenomas**

#### Schema

#### **Patient Population:** (See Section 3.0 for Eligibility)

Patients must have biopsy proven pan-invasive pituitary macroadenomas of the pituitary gland. Pan-invasive for the purposes of the protocol will be defined as meeting each of the following 2 major criteria:

1. tumor volume greater than 20 cc at enrollment, and
2. suprasellar extension.

In addition, a pan-invasive tumor must meet any one of the following 3 minor criteria:

- a) unresectable tumor invasion into a cavernous sinus,
- b) bone or bone marrow invasion into the clivus or temporal bones, or
- c) tumor extension in any direction unlikely to be completely removed specifically by a transphenoidal surgical approach.

Patients who meet the two major criteria above (1 and 2) and are medically inoperable for tumor resection (due to confounding co-existing medical problems) are eligible without meeting any of the three minor criteria (a, b, or c).

Patients should be immediately threatened for vision loss or other significant neurological impairment directly related to tumor mass effect. As such, all patients enrolled would likely benefit from tumor response (shrinkage).

Patients with pituitary carcinomas are not eligible.

Number of patients = up to 12 in each or two cohorts listed below (total up to 24).

Patients will be divided into two cohorts depending on if they have been previously treated with radiotherapy or not.

Eligible patients may have a functioning or non-functioning adenoma and may have previously undergone a surgical resection for their adenoma.

The goal of the study is primarily to monitor for tumor shrinkage after seed implantation. Additional outcomes that will be monitored are change in visual fields, potential toxicities (acute and late) related to the treatment, progression free survival, and changes in patient reported outcomes.

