## 1.5 **Description of protocol therapy**

- 1.5.1 This study is a single arm Phase II pilot trial. Patients enrolled on the trial will undergo implantation of high activity iodine-125 seeds into their pituitary adenoma as outlined in sections 6 and 7. The tumor response to treatment will be monitored as well as change in visual fields, associated adverse effects, progression free survival and patient reported outcomes.

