2.2.2.2 Timeframe of assessment is up to 5 years post therapy

2.2.3 To determine the progression free survival

2.2.3.1 Timeframe of assessment is up to 5 years post therapy

2.2.4 To determine the effect of the treatment on quality of life evaluations (patient reported outcomes)

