2.2.5.1 Timeframe of assessment is up to 5 years post therapy

## **3        PATIENT SELECTION**

### **3.1      Inclusion Criteria**

3.1.1 Pathological or radiographic diagnosis of a pan-invasive pituitary macroadenoma

3.1.2 Pan-invasive for the purposes of the protocol will be defined as meeting each of the following 2 major criteria: 1. tumor volume greater than 20 cc at enrollment, and 2. suprasellar extension. In addition, a pan-invasive tumor must meet any one of the following 3 minor criteria, a) unresectable tumor invasion into a cavernous sinus, b) bone or bone marrow invasion into the clivus or temporal bones, or c) tumor extension in any direction unlikely to be completely removed by specifically a transsphenoidal surgical approach.

3.1.3 Patients who meet the two major criteria above (1 and 2) and are medically inoperable for tumor resection (due to confounding co-existing medical problems) are eligible without meeting any of the three minor criteria (a, b, or c).

3.1.4 Patients should be immediately threatened for vision loss or other significant neurological impairment directly related to tumor mass effect. As such, all patients enrolled would likely benefit from tumor response (shrinkage).

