3.1.5 Patients must have visible tumor on imaging studies (MRI or CT)

3.1.6 The patient's Zubrod performance status must be 0-3.

3.1.7 Patients must be at least 18 years of age.

3.1.8 **Mandatory Imaging Studies:** Must be done 45 or fewer days prior to study entry

3.1.8.1 MRI or CT scan of the brain including the entire skull base and all areas of tumor extension

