#### 11.2.3 Progression Free Survival

#### 11.2.4 Change in QOL Assessments

11.2.4.1 Scoring of each assessment tool will be conducted as per each individual tool's scoring instructions

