11.5 Analysis Plan

11.5.1 Interim Reports

11.5.1.1 Interim reports will be updated at least every six months until the results of the study are published. In general, the interim reports will contain information about patient accrual rate with projected completion dates of the trial, status of QA review and compliance rate of treatment per protocol, and the frequencies and severity of toxicity.

11.5.1.2 *The Analysis of Tumor Shrinkage:* This analysis will be carried out when each patient has had at least 730 days (i.e., 24 months) of follow-up. The percent change in size and volume of the adenoma will then be calculated by subtracting the post-treatment measurements from the pre-treatment measurements then divided by the pre-treatment measurements and then multiplied by 100. The mean, median and standard deviation of the percent change will be determined.

11.5.1.3 *Estimation of Secondary Endpoints Related to the Efficacy:* Cumulative incidence approach will be used to estimate the progression free survival. For any individual patient, progressive disease (PD) within the treated lesion will be scored as PD for that patient

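### Section 11.5.1.3 estimates progression-free survival by a cumulative incidence approach, names only treated-lesion progression as an event, and does not say how death without progression is handled

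*Combined protocol and SAP*

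**What the plan says.** The analysis plan for PFS is two sentences in section 11.5.1.3. The first gives the method: "Cumulative incidence approach will be used to estimate the progression free survival". The second gives the event: "progressive disease (PD) within the treated lesion will be scored as PD for that patient". Death is not mentioned.

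The other places that name the endpoint add no definition:

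- The Study Synopsis lists it among the monitored outcomes: "progression free survival, and changes in patient reported outcomes".
- Section 1.5.1 does the same: "associated adverse effects, progression free survival and patient reported outcomes".
- Section 2.2.3 makes it a secondary objective, "To determine the progression free survival", assessed for up to 5 years.
- Section 11.2.3 is a heading with no text beneath it: "11.2.3 Progression Free Survival".

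Appendix VI uses a related term, freedom from progression, for the cost-utility work, and it too has no rule for death. Death otherwise appears in the safety reporting rules (section 6.9) and as a grade on the performance scales (Appendix II), not in an efficacy definition.

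**The concern.** The label and the method point to different quantities. PFS conventionally counts death from any cause as an event. A cumulative incidence curve for progression conventionally treats death as a competing event, so a patient who dies without progression stays on the favourable side of one minus the curve. A reader given a PFS percentage from this trial could not tell which was meant.

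The difference matters only if someone dies without progression during follow-up. The entry criteria make that possible. Under section 3.1.3, patients who meet the two major criteria and "are medically inoperable for tumor resection (due to confounding co-existing medical problems) are eligible" without any minor criterion, and section 3.1.6 says: "The patient's Zubrod performance status must be 0-3". The documents give no death rate. If the choice stays open, it could be made after the deaths are known, and any such death makes one minus cumulative incidence look better than PFS.

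**Working it through.** The documents give no PFS rate, event count or margin, so there is no plan figure to reproduce. The inputs from the plan are the cohort size (up to 12, section 11.3.2), the total (at most 24, section 11.3.2) and the 5-year window (section 2.2.3). Event counts and hazards below are assumptions.

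**General relation.** With death competing, one minus the cumulative incidence of progression = PFS + cumulative incidence of death without progression. Each such death adds S(t−)/Y to the gap, where S(t−) is PFS just before the death and Y is the number still at risk.

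**Complete follow-up.** S(t−)/Y reduces to 1/n. Per death: 1/12 = 8.3 points; 1/24 = 4.2 points. With no deaths the gap is 0.

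**Example: n = 12, two progressions, one death without progression, no other censoring.**

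- PFS, death as an event: 9/12 = 75.0%.
- One minus cumulative incidence, death competing: 1 − 2/12 = 83.3%.
- Kaplan-Meier with death censored depends on when the death falls:
  - before both progressions: 10/11 × 9/10 = 81.8%;
  - between them: 11/12 × 9/10 = 82.5%;
  - after both: 11/12 × 10/11 = 83.3%.

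PFS and one minus cumulative incidence do not depend on that order.

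**Incomplete follow-up.** Take progressions at months 12 and 24 and a death at month 36, so S(t−) = 10/12. One minus cumulative incidence stays at 83.3%.

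| Censored at month 30 | At risk at the death | Step | PFS |
|---|---|---|---|
| 0 | 10 | (10/12)/10 = 8.3 | 75.0% |
| 2 | 8 | (10/12)/8 = 10.4 | 72.9% |
| 4 | 6 | (10/12)/6 = 13.9 | 69.4% |

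For scale, the exact (Clopper-Pearson) 95% interval for 9/12 is 42.8% to 94.5%.

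**Expected gap under assumed constant hazards.** With progression hazard hp and death hazard hd per year, PFS at 5 years = exp(−5(hp + hd)) and gap = hd/(hp + hd) × (1 − PFS). For example, hp = 2% and hd = 1% give PFS = exp(−0.15) = 86.07% and gap = (1/3) × 13.93 = 4.64 points. The chance of at least one such death among 12 patients, all followed for 5 years, is 1 − (1 − gap)^12.

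| Assumed hd per year | Gap at 5 years, hp 2–4% | Chance of at least one such death in 12 |
|---|---|---|
| 0 | 0 | 0 |
| 0.5% | 2.2–2.4 points | 24–25% |
| 1% | 4.4–4.6 points | 42–44% |
| 2% | 8.6–9.1 points | 66–68% |

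**The case against.** The strongest reply is that this is a missing definition, not an error. A reader might infer that the plan will overstate PFS. The documents do not support that: section 11.5.1.3 does not exclude a composite event, under which one minus the curve equals PFS. Nor is the method wrong in itself. Cumulative incidence of local progression with death competing is a legitimate quantity, and the treated-lesion sentence and the freedom-from-progression wording in Appendix VI give that reading some support. What stands is that the method named does not ordinarily yield the endpoint named, and the event definition that would reconcile them is absent.

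The second reply is size. PFS has no test, threshold or sample size attached; section 11.3.2 rests on the response rate alone. One death shifts the figure by little compared with an interval of 42.8% to 94.5%. This limits the weight. It does not remove the point, because the interval shows imprecision but cannot show which quantity was estimated.

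Third, the assumed hazards may be pessimistic. Section 1.2 cites PFS of 80–90% at 10 years after conventional radiotherapy. The scenarios with deaths imply exp(−10(hp + hd)), from exp(−0.25) = 77.9% down to exp(−0.60) = 54.9%. That cited population is non-secretory adenomas, not large invasive tumours, so the comparison does not settle the matter. Section 11.4.1 expects the study to finish in three to five years, so not every patient may have 5 years of follow-up. The table is therefore illustrative only.

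Finally, one might infer that all deaths are already captured as grade 5 events whatever their cause. Sections 6.9.1 to 6.9.3 do not clearly guarantee this. The adverse event definition ignores causality but requires a temporal link to treatment. The serious event definition runs to 30 days after protocol treatment. Section 6.9.3.2 covers all deaths up to 30 days after discontinuation, and later events only if probably related. Adverse event assessment is scheduled to year 10 (section 10.1.2), but capture of a late unrelated death is not assured.

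**Conclusion.** The point holds as an undefined event rule attached to a method that does not ordinarily estimate the named endpoint. On the ordinary reading, one minus the curve exceeds PFS by 8.3 points per death without progression in a fully followed cohort of 12 and by 4.2 points in 24; the step is larger if patients are censored before the death. A composite event gives no gap. Censoring deaths gives a third figure, 81.8% to 83.3% in the example, against 75.0% for PFS. If no patient dies without progression, all three agree.

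The silence on death is certain from the text. The size depends on a number of deaths that the documents do not give. The weight is modest because the endpoint is descriptive and secondary, but the change should be made before any such death is known.

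**What to change.** Restate section 11.5.1.3, for example: *PFS is the time from implant to the first of treated-lesion progression or death from any cause, estimated by Kaplan-Meier with a 95% CI; patients without an event are censored at the last tumour imaging assessment.* Imaging must be specified because clinic and MRI visits follow different schedules (Appendix I). The cumulative incidence of local progression, with death competing, may be reported separately under that name.

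Alternatively, keep the method, name death as the competing event, and rename the endpoint cumulative incidence of local progression in the Study Synopsis and sections 1.5.1, 2.2.3, 11.2.3 and 11.5.1.3. That would be consistent with the freedom-from-progression wording in Appendix VI.

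Either way, record date of death or last known vital status for every patient at the scheduled follow-ups. The measurement criterion for progression is a separate matter that the sponsor also needs to state.

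The cost is a wording change and one extra data item. Under the first option, the reported PFS will be lower if a patient dies without progression. The second avoids the lower figure but gives up PFS as an endpoint.

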11.6 Gender and Minorities

11.6.1 In conformance with the National Institute of Health Revitalization Act of 1993 with regard to inclusion of women and minorities in clinical research, we have also considered the possible interaction between race and treatments. The projected gender and minority accruals are:

**Projected Distribution of Gender & Minorities**

| Ethnic Category                    | Sex/Gender |       |           |
|---|-------------------|-------|-----------|
|   | Females           | Males | Total     |
| Hispanic or Latino                        | 4                 | 4     | 8         |
| Not Hispanic or Latino                    | 4                 | 12    | 16        |
| Ethnic Category: Total of all subjects    | 8                 | 16    | 24 |
| Racial Category                    |                   |       |           |
| American Indian or Alaskan Native         | 0                 | 0     | 0         |
| Asian                                     | 0                 | 2     | 2         |
| Black or African American                 | 4                 | 6     | 10        |
| Native Hawaiian or other Pacific Islander | 0                 | 0     | 0         |
| White                                     | 4                 | 8     | 12        |
| More than one race                        | 0                 | 0     | 0         |
| Racial Category: Total of all subjects    | 8                 | 16    | 24 |

**12 DATA SAFETY MONITORING PLAN**

**12.1 Purpose and Scope**

- 12.1.1 The purpose of the Radiation Oncology Data and Safety Monitoring Plan is to ensure that clinical trial data is accurate and valid and to ensure the safety of trial participants.
- 12.1.2 The Radiation Oncology DSMC is charged with developing, implementing, and maintaining the Data and Safety Monitoring Plan. The membership consists of a Medical Director of Clinical Research as well as representation from the following groups: clinical research, nursing, regulatory, pharmacy, physicists, radiation therapists, and faculty. Ad hoc members are contacted to participate as needed

**12.2 Procedures**

- 12.2.1 Clinical trials are assessed for safety on a continual basis throughout the life of the trial. All SAE's and any AEs that are unexpected and possibly/likely related to study participation are reported to UTSW IRB through an electronic research system per UTSW IRB guidelines.
- 12.2.2 All clinical trials are reviewed on monthly basis for enrollment. All local SAEs are reviewed by Radiation Oncology DSMC monthly for severity and attribution. For investigator-initiated trials, all SAEs at affiliated institutions are monitored as local SAEs. The principle investigator and study coordinator will present a study treatment summary and SAEs for review. Source documents will be available for the DSMC members during the review. NCI Common Toxicity Criteria Version 4 will be used for grading and attributing adverse events.
- 12.2.3 If the SAE occurs on a multi-institutional clinical trial coordinated by the Radiation Oncology Clinical Research Office, the Clinical Research Manager or primary coordinator ensures that all participating sites are notified of the event and resulting action, within one (1) working day of the determination.
- 12.2.4 Interim Stopping Rules - Stopping for toxicity or efficacy will be related to dose limiting toxicity as described in the statistical section.

**APPENDIX I**  
**STUDY PARAMETER TABLE**

|   | Pre-Entry | Months Following Treatment |   |   |   |    |    |    |    |    |    |    |    |    |   | Every 12 months for years 4-10 |
|---|-----------|----------------------------|---|---|---|----|----|----|----|----|----|----|----|----|---|--------------------------------|
|   |           | 1                          | 3 | 6 | 9 | 12 | 15 | 18 | 21 | 24 | 30 | 36 | 42 | 48 |   |                                |
| History and Physical Exam                                | X         | X                          | X | X | X | X  | X  | X  | X  | X  | X  | X  | X  | X  | X | X                              |
| MRI Brain  | X         |                            | X | X | X | X  | X  | X  | X  | X  | X  | X  | X  | X  | X | X                              |
| Weight   | X         |                            | X |   |   |    |    | X  | X  | X  | X  | X  | X  | X  | X | X                              |
| Humphrey Visual Field Test                               | X         |                            |   | X |   | X  |    | X  |    | X  |    | X  |    | X  |   | X                              |
| Visual Acuity  | X         |                            |   | X |   | X  |    | X  |    | X  |    | X  |    | X  |   | X                              |
| Audiometry   | X         |                            |   |   |   |    |    |    |    |    |    |    |    |    |   |                                |
| Pregnancy test (if applicable)                           | X         |                            |   |   |   |    |    |    |    |    |    |    |    |    |   |                                |
| Endocrinological Evaluation                              | X         |                            |   |   |   | X  |    |    |    | X  |    | X  |    | X  |   | X                              |
| Creatinine, CBC, platelets, PT/INR, PTT, Serum Chemistry |           | X                          |   |   |   |    |    |    |    |    |    |    |    |    |   |                                |
| Neurocognitive Assessment                                | X         |                            |   |   |   | X  |    |    |    | X  |    | X  |    | X  |   | X                              |
| Blood Draw for Translational Research                    |           | X a             |   |   |   |    |    |    |    |    |    |    |    |    |   |                                |
| Informed consent   | X         |                            |   |   |   |    |    |    |    |    |    |    |    |    |   |                                |
| QOL Assessment   | X         |                            |   | X |   | X  |    |    |    | X  |    | X  |    | X  |   | X                              |
| Adverse event evaluation                                 |           | X                          | X | X | X | X  | X  | X  | X  | X  | X  | X  | X  | X  |   | X                              |

a week prior to implant

## APPENDIX II

### ZUBROD PERFORMANCE SCALE

|   |  |
|---|--|
| 0 | Fully active, able to carry on all predisease activities without restriction (Karnofsky 90-100).   |
| 1 | Restricted in physically strenuous activity but ambulatory and able to carry work of a light or sedentary nature. For example, light housework, office work (Karnofsky 70-80). |
| 2 | Ambulatory and capable of all self-care but unable to carry out any work activities. Up and about more than 50% of waking hours (Karnofsky 50-60).                             |
| 3 | Capable of only limited self-care, confined to bed or chair 50% or more of waking hours (Karnofsky 30-40).   |
| 4 | Completely disabled. Cannot carry on self-care. Totally confined to bed or (Karnofsky 10-20).  |
| 5 | Death (Karnofsky 0).   |

### KARNOFSKY PERFORMANCE SCALE

|     |  |
|-----|--|
| 100 | Normal; no complaints; no evidence of disease                                |
| 90  | Able to carry on normal activity; minor signs or symptoms of disease         |
| 80  | Normal activity with effort; some sign or symptoms of disease                |
| 70  | Cares for self; unable to carry on normal activity or do active work         |
| 60  | Requires occasional assistance, but is able to care for most personal needs  |
| 50  | Requires considerable assistance and frequent medical care                   |
| 40  | Disabled; requires special care and assistance                               |
| 30  | Severely disabled; hospitalization is indicated, although death not imminent |
| 20  | Very sick; hospitalization necessary; active support treatment is necessary  |
| 10  | Moribund; fatal processes progressing rapidly                                |
| 0   | Dead   |

## APPENDIX III

### Post-Implant Dosimetry Data Form

Patient:

Physician:

Source: I-125, model XXXX

Doses are based upon TG 43 Dosimetry

Date of Pre-Implant CT study:

Date of Implant:

Date of Post-Implant CT study:

#### Basic Dosimetry Information

1. average activity per seed as measured by institution:
  - Activity:                    mCi                    Date:
2. midpoint apparent activity stated by the vendor:
  - Activity:                    mCi                    Date:
3. number of seeds used:
4. number of needles used:
5. Prescribed dose:            50Gy                    TG 43 dosimetry
6. Peripheral dose:            Gy                    TG 43 dosimetry

### Post Implant CT Analysis

Date of Implant:

Date of Post Implant CT Study:

1. Adenoma is defined on \_\_\_\_ slices.
2. Seeds are defined on \_\_\_\_ slices.

### Analysis of each CT image

| Slice | Min Dose to Adenoma (GTV) in Gy | Dimensions of: High Dose Area (cm x cm) | Low Dose Area (cm x cm) |
|-------|---------------------------------|---|-------------------------|
| 1     |                                 |   |                         |
| 2     |                                 |   |                         |
| 3     |                                 |   |                         |
| 4     |                                 |   |                         |
| 5     |                                 |   |                         |
| 6     |                                 |   |                         |
| 7     |                                 |   |                         |
| 8     |                                 |   |                         |

|    |  |  |  |
|----|--|--|--|
| 9  |  |  |  |
| 10 |  |  |  |
| 11 |  |  |  |
| 12 |  |  |  |

